### 10.3 Best Response

This is calculated from the sequence of objective statuses.

- a. CR: Two or more objective statuses of CR a minimum of four weeks apart documented before progression or symptomatic deterioration.

- b. PR: Two or more objective statuses of PR or better a minimum of four weeks apart documented before progression or symptomatic deterioration, but not qualifying as CR.
- c. Unconfirmed CR: One objective status of CR documented before progression or symptomatic deterioration but not qualifying as CR or PR.
- d. Unconfirmed PR: One objective status of PR documented before progression or symptomatic deterioration but not qualifying as CR, PR or unconfirmed CR.
- e. Stable/no response: At least one objective status of stable/no response documented at least 6 weeks after registration and before progression or symptomatic deterioration, but not qualifying as anything else above.
- f. Increasing disease: Objective status of progression within 12 weeks of registration, not qualifying as anything else above.
- g. Symptomatic deterioration: Objective status of symptomatic deterioration within 12 weeks of registration, not qualifying as anything else above.
- h. Inadequate assessment, response unknown: Progression or symptomatic deterioration greater than 12 weeks after registration and no other response category applies.

10.4 Performance Status:

Patients will be graded according to the Zubrod Performance Status Scale.

| POINT | DESCRIPTION   |
|---------------------|---|
| 0                   | Fully active, able to carry on all pre-disease performance without restriction.   |
| 1                   | Restricted in physically strenuous activity but ambulatory and able to carry out work of a light or sedentary nature, e.g., light housework, office work. |
| 2                   | Ambulatory and capable of self-care but unable to carry out any work activities; up and about more than 50% of waking hours.                              |
| 3                   | Capable of limited self-care, confined to bed or chair more than 50% of waking hours.   |
| 4                   | Completely disabled; cannot carry on any self-care; totally confined to bed or chair.   |

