**Footnotes:**

- ∑ Protocol treatment and physical, laboratory, and scan parameters will continue at these intervals indicated in the Cycle 2-5 columns until progression of disease or until patient has met any of the guidelines in [Section 7.6](#).
- Ω After off treatment prior to disease progression, scans for disease assessment and physical assessments (with lab tests performed at the discretion of the treating investigator) should take place every 8 weeks until progression.
- % After off treatment following disease progression, physical assessments (with lab tests performed at the discretion of the treating investigator) should take place once every 3 months for three years from the time of registration.
- ι Oral capsule taken twice daily on Days 1-7 of every cycle. Day 3 dose should be taken at treating institution 1 hour ( $\pm$  30 minutes) prior to irinotecan (see [Section 7.2](#)).
- ϕ Infusion to be given on Day 3 of every cycle (see [Section 7.2](#)).
- £ Infusion to be given starting on Day 3 over 46-48 hours (see [Section 7.2](#)).
- α Bolus to be given on Day 1 prior to 46 hour infusion (see [Section 7.3](#)).
- β Infusion to be given on Day 1 of every cycle (see [Section 7.3](#)).
- γ Infusion to be given starting on Day 1 over 46-48 hours (see [Section 7.3](#)).
- δ See [Section 15.0](#) for more information.
- \*\* BUN, alkaline phosphatase, sodium, potassium, calcium, glucose, albumin, chloride, carbon dioxide/bicarbonate
- π Labs do not need to be repeated if pre-study labs were done within 7 days prior to Cycle 1 Day 1.
- \$ CA19-9 should be repeated every 4 weeks if abnormal at baseline. If CA19-9 normal at baseline, CEA must be tested and if CEA is abnormal, should be repeated every 4 weeks.
- △ Women of childbearing potential must have a negative serum or urine pregnancy test at screening within 28 days prior to registration. If randomized to Arm 1, serum or urine pregnancy tests are required within 72 hours prior to the first dose of study treatment. At discontinuation, a pregnancy test must be done within 4 weeks after the last dose of study drug. A pregnancy test should be done at any time there are clinical concerns for possible pregnancy.

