### 10.7 Duration of Response (DoR)

From date of first documentation of response (CR or PR) to date of first documentation of progression or symptomatic deterioration (as defined above), or death due to any cause among patients, who achieve a response (CR or PR). Patients last known to be alive without report of progression are censored at date of last contact.

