#### 14.4 Data Submission Overview and Timepoints

- a. DAY OF BLOOD DRAW (before or within 5 days after registration prior to treatment):

Submit the following:

Blood specimen as outlined in [Section 15.1c](#).

- b. WITHIN 7 DAYS OF REGISTRATION:

Submit the following:

**S1513** Onstudy Form

**S1513** Baseline Abnormalities Form

Baseline Tumor Assessment Form (RECIST 1.1)

Pathology Reports: Initial diagnosis, metastatic (if done), and fresh biopsy (NOTE: Upload reports via the Source Documentation: Baseline form in Rave®.)

Submit radiology reports from all scans performed to assess disease at baseline. (NOTE: Upload reports via the Source Documentation: Baseline form in Rave®.)

c. WITHIN 28 DAYS OF REGISTRATION:

Tissue specimens as outlined in [Sections 15.1](#) and [15.2](#).

d. WITHIN 14 DAYS AFTER EACH CYCLE OF TREATMENT:

Submit the following:

**S1513** Treatment Form

**S1513** Adverse Event Form

e. WITHIN 14 DAYS AFTER EACH CA19-9 OR CEA TEST (every 4 weeks):

Submit the following:

**S1513** CA19-9 (CEA) Form

f. WITHIN 14 DAYS AFTER EACH DISEASE ASSESSMENT (INCLUDING BOTH ON TREATMENT AND OFF TREATMENT PRIOR TO DISEASE PROGRESSION):

Submit the following:

Follow Up Tumor Assessment Form (RECIST 1.1)

Radiology reports from all scans performed to assess disease (NOTE: Upload reports via the Source Documentation: Follow-up form in Rave®.)

g. WITHIN 14 DAYS OF DISCONTINUATION OF TREATMENT:

Submit the following:

Off Treatment Notice

**S1513** Treatment Form

**S1513** Adverse Event Form

h. WITHIN 14 DAYS OF PROGRESSION/RELAPSE:

Submit the following:

Follow-up Tumor Assessment Form (RECIST 1.1)

Off Treatment Notice (if the patient was still on protocol treatment)

Final **S1513** Treatment Form (if the patient was still on protocol treatment)

Final **S1513** Adverse Event Form

Follow-Up Form (if the patient was off protocol treatment) documenting date, site and method for determining progression/relapse.

Radiology Reports (NOTE: Upload reports via the Source Documentation: Follow-up form in Rave®.)

i. AFTER OFF ALL PROTOCOL TREATMENT, EVERY 3 MONTHS UNTIL 3 YEARS FROM REGISTRATION:

Submit the following:

Follow Up Form

Late Adverse Events Form (if prior to treatment for progression or relapse or a second primary, and prior to non-protocol treatment, the patient experiences any severe [Grade  $\geq$  3] long term toxicity that has not been previously reported)

j. WITHIN 4 WEEKS OF KNOWLEDGE OF DEATH:

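### Best response has no cut-off at the start of other anticancer therapy, so a scan on another regimen can count towards the assigned arm's ORR and DCR

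*Combined protocol and SAP*

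**What the plan says.** Section 10.3 introduces best response with "This is calculated from the sequence of objective statuses". Each favourable category then has the same end-point. Confirmed PR requires "Two or more objective statuses of PR or better a minimum of four weeks apart documented before progression or symptomatic deterioration". Unconfirmed PR, which section 1.2c counts as a response, requires only "One objective status of PR documented before progression or symptomatic deterioration but not qualifying as CR, PR or unconfirmed CR". Stable disease requires "At least one objective status of stable/no response documented at least 6 weeks after registration and before progression or symptomatic deterioration". None of these refers to the end of protocol treatment or to the start of another therapy, and section 11.4, which sets out the ORR and DCR analyses, adds no such rule.

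Scanning does not end with protocol treatment. A footnote to the section 9.0 calendar begins "After off treatment prior to disease progression, scans for disease assessment and physical assessments" and sets an 8-week interval until progression. Section 14.4f requires tumour assessment forms for these visits, "INCLUDING BOTH ON TREATMENT AND OFF TREATMENT PRIOR TO DISEASE PROGRESSION".

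Duration of response in section 10.7 runs "From date of first documentation of response (CR or PR) to date of first documentation of progression or symptomatic deterioration", or to death, again without reference to new therapy. The plan uses the start of other treatment as a limit in one place only. Section 14.4i asks for the Late Adverse Events Form when a severe late toxicity occurs "prior to treatment for progression or relapse or a second primary, and prior to non-protocol treatment".

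**The concern.** ORR and DCR are normally read as the activity of the assigned regimen. Under section 7.6 a patient can leave protocol treatment without progression, because of toxicity, a delay of more than four weeks, or withdrawal. If that patient starts another regimen and the next scan shows stable disease or a partial response, section 10.3 as written places the result in the assigned arm.

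Three uses are exposed:
- the chi-square comparisons of ORR and DCR in section 11.4;
- the biomarker associations with ORR in section 11.5;
- the ROC analysis in section 11.5, which uses overall disease response to set an HRD score threshold.

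In the last two, a response obtained on a different drug is a wrong label for sensitivity to the assigned regimen. With few responders expected, a handful of such labels could matter.

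**Working it through.** **1. The plan's own figure.** Section 11.4 says that 64 eligible patients per arm estimate the response rate to within 13% (95% confidence interval). At a rate of 50%, 1.96 × √(0.25/64) = 12.25 points. The largest one-sided distance of the exact (Clopper-Pearson) interval over all possible counts is 13.0 points. The figure is reproduced. The point concerns a definition and disputes no stated number.

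**2. Can such a scan arise under the text?**
- Scans are every 8 weeks on treatment (calendar footnote c), and stable disease needs one status at 6 weeks or later. A patient who stops before week 8 will ordinarily have no qualifying status yet.
- Some exits are immediate: withdrawal (7.6d) and Grade 4 non-haematologic toxicity of the kind covered by 8.4i.
- Other exits are slow. Many toxicities lead first to a hold of up to four weeks and stepped reductions (8.3, 8.4). A patient held from weeks 3–4 who does not recover leaves at about weeks 7–8, when the first scan is due.
- Patients who stop because of global decline are already cut off by symptomatic deterioration (10.2e).

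The route exists, but it is narrow.

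**3. How far would a cut-off move each rate?** Let f be the share of an arm that leaves protocol treatment before progression, starts another regimen, is scanned before progression and has no earlier qualifying status. Let q be the chance of a qualifying status on that scan. The rate changes by f × q. The documents give neither f nor q, so the values below are assumptions.

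| Endpoint | f | q | Change in rate | Patients of 64 |
|---|---|---|---|---|
| DCR, low | 5% | 40% | 2.0 points | 64 × 0.05 × 0.40 = 1.3 |
| DCR, high | 15% | 60% | 9.0 points | 64 × 0.15 × 0.60 = 5.8 |
| ORR, low | 5% | 10% | 0.5 points | 64 × 0.05 × 0.10 = 0.3 |
| ORR, high | 15% | 20% | 3.0 points | 64 × 0.15 × 0.20 = 1.9 |

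One response is 1/64 = 1.6 points. At the 10% null ORR of section 11.5, an arm of 64 expects 6.4 responders. Section 11.5 expects 46 assayed patients per arm, so 0.10 × 46 = 4.6 responders. One mislabelled response would be 1/4.6, or about 22% of that number.

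**4. Would the comparison between arms be distorted?** Only if f × q differs between arms. Take a true DCR of 50% in both arms, q = 50%, 64 per arm, and a two-sided 5% chi-square test without continuity correction (all assumed).
- f of 10% against 5%: observed rates 55.0% and 52.5%, a spurious difference of 2.5 points, rejection probability 5.9%.
- f of 15% against 5%: observed rates 57.5% and 52.5%, a spurious difference of 5.0 points, rejection probability 8.8%.

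With equal f and q in the two arms there is no spurious difference. Exchanging the arms reverses its sign.

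**The case against.** The strongest reply is that this is a coherent treatment-policy choice. OS is analysed by intention to treat, PFS runs to progression or death without censoring at new therapy, and scanning continues after treatment stops. Counting every status before progression fits that pattern. This is a fair defence for OS and PFS. For ORR and DCR the plan does not state the choice, and an all-scan sensitivity analysis preserves that reading. For duration of response the reply largely stands: censoring it at new therapy while PFS runs on would handle the same progression under two rules.

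A second reply is that the cut-off creates its own asymmetry. A patient who switches before the first scan is scored as without disease control, even if the disease was stable when treatment stopped. That counts against an arm with more early toxicity stops. This is correct and has to be stated as a cost.

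A third is that a response is unlikely to arise this way. Most patients already have one metastatic regimen behind them (5.2), and PR needs a 30% fall from the original baseline without intervening progression (10.2b). This is also fair, and it is why the effect on ORR is probably smaller than on DCR.

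Some stronger readings are tempting but unsupported:
- A reader might infer that DCR is overstated by 2–9 points in favour of the arm with more toxicity stops. Both rates are assumed, nothing shows which arm would switch more, and a stable week-8 scan may partly reflect protocol cycles already given. The 2–9 points are an amount reclassified, not an established bias.
- A reader might infer from 14.4i that the forms already capture the date needed, or that the plan has accepted this boundary as right for efficacy. That clause only conditions submission of a late-toxicity form.

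Section 10.0 cites RECIST 1.1, but the protocol text takes no rule on new therapy from it.

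**Conclusion.** The gap is real but limited. As written, section 10.3 allows a response or stable status obtained on another regimen to count for the assigned arm, and nothing in sections 10 or 11 prevents it. On the assumed rates above, DCR would change by about 2–9 points and ORR by about 0.5–3 points. The true size may lie outside these ranges, and the between-arm direction cannot be determined from the documents.

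Only secondary and translational endpoints are involved. The primary OS analysis does not use best response. Nor does the interim futility rule, which rests on PFS. A rule confined to statuses before other therapy is the better primary definition for endpoints meant to describe regimen activity, and it should be stated before those endpoints are analysed.

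**What to change.** - In 10.3 and 11.4, state that ORR, DCR and the response labels in 11.5 (biomarker associations and the HRD-threshold ROC analysis) count only objective statuses dated before the start of any non-protocol anticancer therapy.
- Keep patients with no qualifying status before that date in the denominator, as non-responders without disease control.
- Report ORR and DCR from all scans before progression as a sensitivity analysis, with the number of patients per arm whose category differs between the two versions.
- Leave PFS as defined in 10.5 and the main duration-of-response definition in 10.7. Report duration of response censored at new therapy only as a sensitivity analysis.
- Confirm that the start date of non-protocol anticancer therapy is recorded for every patient. If it is not, it has to be collected, which is more work than a change of wording.

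The Revision #1 memorandum says that accrual is closed and all patients are off treatment. The change therefore affects only how scans are classified, and no patient procedure. The sample size and the stated precision are unchanged. The cost is that ORR and DCR may be slightly lower, and that early switchers count as without disease control, which can weigh on an arm with more early toxicity stops. The all-scan analysis shows how much that matters.

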10.5 Progression-Free Survival

From date of registration to date of first documentation of progression or symptomatic deterioration (as defined above), or death due to any cause. Patients last known to be alive without report of progression are censored at date of last contact.

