### 11.3 Interim Analysis

An interim futility analysis of progression-free survival (PFS) by treatment arm will be performed by testing an alternative hypothesis of a 1.5 HR at  $p < 0.05$  when approximately 35% of the expected PFS events in the control arm have been observed. We expect this analysis to occur when approximately 50% of the study sample has been accrued. Unless there are toxicity concerns or extenuating circumstances, the study will not close during this interim assessment. If this alternative hypothesis is rejected at  $p < 0.05$  then the study may be closed to further accrual and the experimental agent declared of no interest for further development. If we fail to reject this hypothesis, the study will complete accrual.

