Assuming a baseline median PFS of 3 months, the following table shows approximate power to detect PFS hazard ratios of 2.5, 3, and 3.5, corresponding to median PFS of 7.5, 9, and 10.5 months in the biomarker-positive subgroup, using a two-sided alpha of 0.1, for a range of biomarker frequencies.

| Biomarker Prevalence | Power    |        |          |
|----------------------|----------|--------|----------|
|                      | HR = 2.5 | HR = 3 | HR = 3.5 |
| 5%                   | 35%      | 43%    | 50%      |
| 10%                  | 54%      | 65%    | 73%      |
| 25%                  | 82%      | 91%    | 95%      |
| 50%                  | 91%      | 97%    | 99%      |

Assuming a null ORR of 10%, the following table describes the approximate power to detect differences in response rate of 25%, 30%, and 35% (corresponding to ORR of 35%, 40%, and 45%) in the biomarker-positive sub-group, using a two-sided 0.1 level test of proportions across a range of biomarker frequencies.

| Biomarker Prevalence | Power           |                 |                 |
|----------------------|-----------------|-----------------|-----------------|
|                      | $\Delta = 25\%$ | $\Delta = 30\%$ | $\Delta = 35\%$ |
| 10%                  | 20%             | 30%             | 39%             |
| 25%                  | 44%             | 56%             | 67%             |
| 50%                  | 50%             | 64%             | 76%             |

We also plan to estimate an HRD score threshold for positivity in this population by applying receiver operating characteristic curves, classifying patients by overall disease response. The precision of this estimate will depend not only on the number of patients with available data but also on the prevalence of disease response.

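### Censoring PFS and duration of response at last contact counts unscanned time as progression-free: it inflates each arm's PFS, and biases the arm comparison only if scan loss differs between arms

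*Combined protocol and SAP*

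**What the plan says.** Section 10.5 defines PFS as running "From date of registration to date of first documentation of progression or symptomatic deterioration (as defined above), or death due to any cause". For everyone else: "Patients last known to be alive without report of progression are censored at date of last contact". Section 10.7 repeats that sentence for duration of response, and Section 10.6 uses the same date for overall survival.

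Other parts of the document bear on this:

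- Section 10.2 says that scanning beyond the target areas is needed to establish that progression is absent. Section 10.2f classes a patient with unassessed target lesions, and no documented progression or symptomatic deterioration, as inadequately assessed with unknown status.
- The footnotes to the Section 9.0 calendar require scans every 8 weeks on treatment and ask for them every 8 weeks off treatment until progression.
- Section 14.4i sets a separate contact schedule that is not tied to a scan: "AFTER OFF ALL PROTOCOL TREATMENT, EVERY 3 MONTHS UNTIL 3 YEARS FROM REGISTRATION".
- Section 11.3 bases its interim look on PFS: "An interim futility analysis of progression-free survival (PFS) by treatment arm will be performed by testing an alternative hypothesis of a 1.5 HR", "when approximately 35% of the expected PFS events in the control arm have been observed".

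There is no rule for missed scans or for new therapy before progression, and no sensitivity analysis of PFS is planned.

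**The concern.** Last contact is the right censoring date for survival, because contact establishes the endpoint. It does not establish that a patient is free of progression. Someone who stops treatment for toxicity, a long delay or personal choice (Section 7.6), and then misses scans, can go on generating follow-up forms. Section 10.5 keeps that patient at risk and progression-free up to the latest form.

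The plan takes median PFS to be short ("Assuming a baseline median PFS of 3 months", Section 11.5), so a few unscanned months can hide a real progression. At stake are the per-arm PFS estimates, the PFS comparison in Section 11.4, the biomarker analyses of PFS in Section 11.5, duration of response and, if scan loss is unequal, the interim look.

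**Working it through.** **1. The plan's interim timing reproduces.** Take exponential PFS with median 3 months (λ = ln 2 / 3 = 0.2310 per month), 64 eligible patients per arm and uniform accrual over 28 months. At month 14, 32 control patients are enrolled.

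- Control events by month 14: 32 × [1 − (1 − e^(−14λ)) / (14λ)] = 22.5.
- Control events by month 38: 64 × [1 − (e^(−10λ) − e^(−38λ)) / (28λ)] = 63.0.
- Ratio: 22.5 / 63.0 = 35.7%, which matches the plan's 35% at half accrual.

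**2. Per-arm effect, in closed form.** Scans fall at 1.84, 3.68 and 5.52 months (8-week steps). A median of 2.0 months from progression to death (μ = ln 2 / 2 = 0.3466) reproduces the 6-month control median OS of Section 11.1. Scan loss of 10% a month is an assumption: the chance of having stopped scans by time s is 1 − e^(−0.1s).

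The probability of progressing in (a, b] and being alive at 6 months is λe^(−6μ)[e^((μ−λ)b) − e^((μ−λ)a)] / (μ − λ) = 0.25[e^(0.1155b) − e^(0.1155a)].

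| Progression interval (months) | Alive at 6 months | Scans stopped before next scan | Unseen |
|---|---|---|---|
| 0–1.84 | 0.059 | 0.168 | 0.010 |
| 1.84–3.68 | 0.073 | 0.308 | 0.023 |
| 3.68–5.52 | 0.091 | 0.424 | 0.038 |
| 5.52–6 | 0.027 | no scan yet due | – |

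- Complete imaging: e^(−6λ) + 0.027 = 0.250 + 0.027 = 0.277, or 28%.
- Last-contact rule: 0.277 + 0.071 = 0.348, or 35%.
- Half of the unseen progressions caught clinically: 0.277 + 0.071/2 = 0.312, or 31%.

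A simulation of the look at month 14 with the same loss rate gave 37% under last contact and 27% under last assessment, against 28%. With half caught clinically it gave 33% and 25%. The last-contact figure rises with the post-progression survival assumed.

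**3. Arm comparison at the interim look.** HR is control over Arm 1, so values above 1 favour Arm 1. With d = 41 to 45 events, the alternative is rejected when the observed log HR is below ln 1.5 − 1.645 × 2/√d, an HR of 0.90 to 0.92. At true HR 1.0 that happens 36 to 39% of the time by the usual approximation, and about 30% in simulation on the 8-week grid (4,000 runs per row, 32 patients per arm, one-sided 0.05). All loss rates are assumptions.

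| True HR | Monthly loss, Arm 2 / Arm 1 | Unseen progression caught | Last contact: HR, stop | Last assessment: HR, stop |
|---|---|---|---|---|
| 1.0 | 0 / 0 | none | 1.00, 30% | 1.00, 30% |
| 1.0 | 10% / 10% | none | 0.99, 32% | 0.99, 32% |
| 1.0 | 5% / 10% | none | 1.03, 28% | 0.96, 34% |
| 1.0 | 0 / 10% | none | 1.10, 22% | 0.94, 36% |
| 1.0 | 10% / 5% | none | 0.96, 36% | 1.03, 28% |
| 1.0 | 0 / 10% | half | 1.00, 32% | 0.90, 44% |
| 1.5 | 0 / 0 | none | 1.54, 3.9% | 1.54, 3.9% |
| 1.5 | 5% / 10% | none | 1.59, 3.8% | 1.43, 6.2% |
| 1.5 | 0 / 10% | none | 1.68, 2.7% | 1.38, 8.6% |
| 1.5 | 0 / 10% | half | 1.53, 5.0% | 1.30, 10.7% |

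A second model, without clinical detection and with 20% of Arm 1 and 10% of Arm 2 stopping scans within 3 months, gave a stopping chance at HR 1.0 of 38% with complete imaging, 31% under last contact and 38% under last assessment. The direction agrees; whether last-assessment censoring returns the look to its complete-imaging behaviour depends on the model.

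**4. Final analysis.** At about 110 deaths among 128 patients, at most 128 − 110 = 18 patients (14%) are alive, and only their times can change with the rule.

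**The case against.** Several points on the other side stand.

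- **Scans do not stop by design.** The calendar asks for 8-weekly scans off treatment until progression in both arms, and Section 14.4h collects the date and method of any progression found off treatment. Scan loss would be a departure from the schedule, at a rate nobody has stated.
- **Unseen progression is not always missed.** Symptomatic deterioration, physician-judged progression of non-measurable disease, and death all end PFS. With half of unseen progressions caught, the effect on the futility look largely disappears under last contact (32% against 30%). How much is caught off treatment is uncertain, because Section 10.2e ties symptomatic deterioration to stopping treatment.
- **The alternative is not neutral.** Censoring survivors at the last scan while still counting later deaths works against the arm with more scan loss.

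A reader might infer that the rule masks an inactive agent at the futility look. The documents do not support that. It needs heavier scan loss in Arm 1, and nothing in the plan establishes this: Arm 1 has an extra route off treatment through ABT-888 dose reductions (Section 8.3), but Arm 2 carries the fluorouracil bolus that Arm 1 omits. With equal loss there is no masking, and with more loss in Arm 2 the direction reverses. The consequence of the look is also permissive: "then the study may be closed to further accrual and the experimental agent declared of no interest for further development". The Revision #1 memorandum says that the study is permanently closed to accrual, so that decision is past in any case.

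**Conclusion.** The definition is at odds with the protocol's own account of what shows absence of progression, and it inflates per-arm PFS whenever scans stop before contact does. At an assumed 10% monthly loss, six-month PFS is overstated by about 7 to 9 percentage points, or 3 to 5 if half of the unseen progressions are caught clinically. Lower loss gives less.

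Bias in the comparison of arms is conditional on unequal loss and can run either way. The primary endpoint is untouched. Duration of response shares the rule but gets only Kaplan-Meier estimates, in about 6 responders per arm at the 10% null response rate of Section 11.5 (64 × 0.10), and has no part in the futility look.

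At the final analysis, changing the rule moves little, because most patients have died and deaths are events under either version. An unseen progression is then dated at death under both rules, which is why the handling of deaths after missed scans needs stating as well.

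**What to change.** In Sections 10.5 and 10.7, replace the censoring sentence with: patients alive without report of progression are censored at the date of the last adequate disease assessment, or at registration if there is none. Then:

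- state how a death or a progression that follows missed scans is treated;
- report the last-contact version as a sensitivity analysis, and show both results side by side, with the number of living patients in each arm whose contact outlasts their scans.

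The cost is a few sentences. Section 14.4 already collects tumour assessment forms and radiology reports after each assessment, so no new data are needed.

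The downside is shorter PFS follow-up. At a look at month 14, about 64 × 1.84/14 = 8 patients would not yet have reached a first scan and would be censored at registration unless they had died or progressed clinically. There is also some bias against an arm with heavier scan loss: apparent HR 0.90 to 0.96 at true HR 1.0, and a false-stop risk at HR 1.5 of roughly 6 to 11% against 5%, under the unequal loss rates assumed above. Neither version alone is safe when scan loss is unequal.
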